### 9.10 Prior and Concomitant Therapy

See Section 8.2. Treatments prohibited prior to enrollment are prohibited for the duration of the study.

### 9.11 Treatment Compliance

All doses will be administered by study personnel.

### 9.12 Accountability of Investigational Drug Supplies

The Investigator at each study site will identify trained and experienced personnel to handle the study drug in accordance with the protocol and appropriate GCP and GMP principles. This includes:

- storing the drug in a secure, limited access facility and under the appropriate conditions;
- dispensing and administering study drug only in accordance with the protocol;
- maintaining drug accountability records;
- at the completion of the study, returning or destroying unused study drug in compliance with the written instructions of the Sponsor.

Detailed procedures will be provided in a separate Pharmacy Manual for this study.

# **10. STUDY EVALUATIONS**

### Detailed schedules of evaluations are shown in Table 2-2 and Table 2-3.

### 10.1 Medical History and Physical Exam

The Investigator will perform a comprehensive history and physical examination at the Screening visit; any new findings observed at subsequent scheduled and unscheduled examinations will be recorded.

### 10.2 Vital Signs

Vital signs include temperature, heart rate (HR), respiratory rate (RR) and blood pressure (BP). Where feasible, vital signs should be measured before blood is drawn and after the patient has been sitting comfortably for  $\sim$ 5 min with the BP cuff in place (preferably on the non-dominant arm). BP and HR measurements may be done manually or by automated recorder. Temperature will be obtained using an electronic (rapid reading) device. Respiratory rate will be determined by observation for at least 30 sec.

#### 10.3 Laboratory Studies

The laboratory tests indicated below will be performed by a CLIA-approved laboratory proposed by the Investigator at each site and approved by the Sponsor. Details of procedures for collecting, processing, storing and shipping the blood samples will be provided in a separate Laboratory Manual.

The Investigator may order additional local laboratory tests consistent with their routine standard of care.

#### 10.3.1 Safety Laboratory Tests

#### Table 10-1. Hematology Panel

Hemoglobin Hematocrit Total red blood cell count Mean cell hemoglobin Mean cell hemoglobin concentration Mean cell volume White blood cell count Platelet count	White blood cell differential (if WBC abnormal) - Neutrophils - Lymphocytes - Monocytes - Eosinophils - Basophils
--	--

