**Confidential and Proprietary** 

[name] 5/31/15 10:25 AM Deleted: Table 2-3. Schedule of Study

[name] 5/31/15 10:25 AN

Deleted: Table 2-2. Schedule of Study

Events - Screening Through Day 74

Events – Dose #3 to End-of-Study Visit

[name] 5/31/15 10:25 AM Deleted: 15.3 [name] 5/31/15 10:26 AM Formatted: Font:Bold

[name] 5/31/15 10:26 AM Formatted: Font:Bold [name] 5/31/15 10:25 AM Deleted: 8.3 [name] 5/31/15 10:25 AM Deleted: 8.3 [name] 5/31/15 10:26 AM Formatted: Font:Bold

- 3. Has a history of active tuberculosis;
- 4. Has previously received another investigational vaccine against tuberculosis;
- 5. Has received any investigational drug during the prior three (3) months;
- 6. Has had surgery requiring general anesthesia during the prior three (3) months;
- 7. Has lost >500 ml of blood (by any process, including donation) during the prior three (3) months;
- 8. Has received systemic immune suppressive or stimulatory prescription drugs during the prior three (3) months;
- 9. Has participated in any biomedical research protocol during the prior one (1) month;
- Has used any prescription or over-the-counter medication during the prior one (1) month, unless approved by both the Investigator and the Sponsor;
- 11. Has had an illness consistent with acute viral or bacterial infection within the prior (2) two weeks;
- 12. If IGRA-positive, has a chest x-ray with any findings consistent with active tuberculosis;
- 13. Has a positive test for hepatitis B surface antigen (HBsAg) or for antibody to hepatitis C virus (HCV) [HIV-negative subjects only; HIV-positive subjects are not excluded for prior hepatitis B or C]
- 14. Has confirmed results on a screening laboratory test (hematology, coagulation, chemistry, urinalysis) that represent Grade 1 or greater abnormalities (tests with abnormalities may be repeated once);
- 15. Has a calculated creatinine clearance of <80 mL/min (based on the Cockcroft-Gault equation);
- 16. Has, within the past 10 years, had evidence of or required treatment for cancer (except treated basal or squamous cell carcinoma of the skin, or cured cervical carcinoma-in-situ);

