#### 2.5.4 Additional / Alternative Exclusion Criteria for HIV-positive Subjects

- 1. Has a history of an AIDS-defining opportunistic infection;
- 2. Has had a CD4 count <200/uL at any time in the past year;
- 3. Has confirmed results on a screening laboratory test (hematology, coagulation, chemistry, urinalysis) that represent Grade 2 or greater abnormalities (tests with abnormalities may be repeated once).

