# 7.5.1 Definition of a Dose-Limiting Toxicity (DLT) Event

A DLT systemic clinical event is defined as a treatment-emergent systemic clinical event that meets **all** of the following criteria:

- is assessed by the investigator as related or possibly related to study drug (see Section 12.3.3);
- is of severity (see Section 12.3.4) Grade 2 or higher;
- is of duration >48 hours.

A DLT injection site reaction (ISR) is defined as an event that meets both of the following criteria:

- occurs at the injection site;
  - is of severity Grade 3 or higher.

A DLT *laboratory event* is defined as a confirmed, treatment-emergent laboratory finding that meets **both** of the following criteria:

- is *not* considered consistent with a concurrent clinical event that is assessed as not related or unlikely related to study drug (e.g., an accidental injury, new ART); *and*
- based on pre-specified toxicity criteria (see Section 12.5.5), represents an increase of two Grades or more compared to pre-treatment baseline value.

A subject who experiences a DLT event will not receive further doses of study drug. Unblinding may be performed to determine if a DLT event has occurred in a subject receiving DAR-901.

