### 12.6 Grading of Specific Laboratory Safety Tests for Reporting and Analysis

For specific laboratory safety tests shown in Table 20-1, all abnormal results will be graded using the criteria shown, which are taken from the "FDA Guidance for Industry. Toxicity Grading Scale for Healthy Adult and Adolescent Volunteers Enrolled in Preventive Vaccine Clinical Trials. September 2007."[20].

The grading will be used both in reporting AEs and in the data presentation and analysis of laboratory results. Specifically, the data listings will indicate the appropriate Grade and treatment-emergent changes in these laboratory tests will be summarized as "shift tables" using these grades (see Section 14.4). This process will assure that the final study report contains complete and consistent analyses of these laboratory safety results.

Treatment-emergent abnormal laboratory results for analytes not shown in Table 20-1, will be reported as AEs using the procedures and criteria detailed in Section 12.1.5.

[name] 5/31/15 10:25 AM **Deleted:** Table 20-1

[name] 5/31/15 10:25 AM **Deleted:** Table 20-1

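### Running the white-cell differential only when total WBC is abnormal leaves most subjects without baseline neutrophil, lymphocyte or eosinophil counts

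*Protocol*

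**What the plan says.** Protocol Section 10.3.1, Table 10-1, lists neutrophils, lymphocytes, monocytes, eosinophils and basophils under an entry that begins "White blood cell differential (if WBC abnormal". The rest of the haematology panel, including total WBC, haemoglobin and platelets, carries no such condition. Section 10.3 allows the investigator to order extra local tests under routine care, but nothing schedules a differential for every subject.

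Four other parts of the protocol bear on this:

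- **Eligibility.** Section 2.5.2, exclusion 14, removes HIV-negative subjects with confirmed screening laboratory results "that represent Grade 1 or greater abnormalities". Section 2.5.4 sets the threshold for HIV-positive subjects at Grade 2, so Grade 1 results are allowed in that group.
- **Laboratory DLT.** Under Section 7.5.1 a qualifying finding "represents an increase of two Grades or more compared to pre-treatment baseline value".
- **Grading and shift tables.** For the tests in Table 20-1, Section 12.6 says that "all abnormal results will be graded using the criteria shown" and that "treatment-emergent changes in these laboratory tests will be summarized as" shift tables by grade. Abnormal treatment-emergent results in analytes outside Table 20-1 go to adverse event reporting through Section 12.1.5.
- **Laboratory adverse events.** Section 12.1.1 counts a new or increased abnormal laboratory result after treatment as an adverse event.

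Safety is the primary objective (Section 6.1), and Section 14.4 names haematology within the primary endpoint.

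**The concern.** A change from baseline needs a count before treatment and a count after it. The reflex rule supplies a count only when a different result, total WBC, is already abnormal, and eligibility selects for people in whom that result is normal. The rule therefore tends to withhold the baseline from the very people who are enrolled.

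After dosing, these counts appear only for subjects with an abnormal total WBC, usually with nothing to compare them with. An isolated fall in neutrophils or rise in eosinophils inside a normal total WBC leaves no record. A report of no such events, by dose level or against placebo, would then reflect the testing rule as much as the vaccine. This is the first clinical use of DAR-901 (Section 5.4), and no analysis plan can recover a count that was not reported.

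**Working it through.** The protocol states no figure for this point, so there is none to reproduce. The check counts who would have a differential.

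**Inputs from the protocol**

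- Table 2-1: cohorts A1-A3 have 3 × 16 = 48 subjects, A4 has 4-6, and B1 and B2 have 5-8 each.
- HIV-negative: 48 + 4 = 52 to 48 + 6 = 54. HIV-positive: 10 to 16. Total: 62 to 70. The HIV-negative share is 52/62 = 84% to 54/70 = 77%.
- Tables 2-2 and 2-3: three safety draws follow the first dose (before Dose #2, before Dose #3, and 28 days after Dose #3).
- Section 14.7: missing data are in general not imputed.

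**Assumption.** Let q be the chance that total WBC is abnormal at a draw. The protocol gives no value, so q is varied from 5% to 20%.

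**Step 1: no baseline differential.** Suppose exclusion 14 leaves no HIV-negative entrant with an abnormal baseline WBC. The share without a baseline differential is then (HIV-negative + HIV-positive × (1 − q)) / total.

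**Step 2: no baseline and post-dose pair.** Drop the reliance on exclusion 14, apply q to everyone, and count one baseline draw. With independent draws the share without a pair is 1 − q × [1 − (1 − q)³]. With full dependence within a subject it is at least 1 − q.

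**Step 3: any post-dose differential.** The share with at least one of three is 1 − (1 − q)³.

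| q | No baseline, N = 62 | No baseline, N = 70 | No pair, independent | No pair, fully dependent | Any post-dose differential |
|---|---|---|---|---|---|
| 5% | 61.5/62 = 99.2% | 69.2/70 = 98.9% | 99.3% | at least 95% | 14% |
| 10% | 61/62 = 98.4% | 68.4/70 = 97.7% | 97.3% | at least 90% | 27% |
| 20% | 60/62 = 96.8% | 66.8/70 = 95.4% | 90.2% | at least 80% | 49% |

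The last column shows that post-dose differentials will exist for some subjects. The scarce item is the baseline.

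**Step 4: what the trigger can miss.** Assume a normal WBC range of 4-10 × 10⁹/L. A WBC of 5.0 with 18% neutrophils gives 5.0 × 0.18 = 0.90 × 10⁹/L. A WBC of 8.0 with 20% eosinophils gives 8.0 × 0.20 = 1.60 × 10⁹/L. Neither sample triggers a differential. These values illustrate the mechanism and say nothing about how often it would occur.

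**Step 5: does the gap depend on Table 20-1?** If Table 20-1 grades a given count, its shift table and its part of the laboratory DLT lack a baseline grade in most subjects. If it does not, Section 12.6 sends that count to adverse event reporting, and Section 12.1.1 asks whether the result is new or increased. That too needs a measured count, and a baseline to judge it against. The gap exists either way. Only the outputs affected differ.

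**The case against.** A reader might infer that the laboratory DLT cannot be derived for nearly all subjects. The documents do not support that. Section 7.5.1 covers every graded analyte, and haemoglobin, platelets, total WBC, chemistry and INR are measured unconditionally. At most the differential components are lost.

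Nor is a contradiction between Table 10-1 and Sections 7.5.1 or 12.6 established. It would require Table 20-1 to grade differential counts, and that table is not in the text available. ANC in the abbreviation list and neutropenia as an example in Table 12-1 are weak evidence: the list also holds terms such as PK that are not scheduled assessments here. A failure to check these counts under exclusion 14 depends on Table 20-1 in the same way.

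It would also be wrong to say that the counts are never produced, since an abnormal WBC triggers them and the investigator may order extra tests.

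The size is partly inferred. Exclusion 14 works on confirmed Grade 1 results, whereas Section 12.1.5 treats out-of-range results as abnormal, and the two need not coincide. A first abnormal result that was normal on repeat could leave a differential on file. The inference is weakest for the 10-16 HIV-positive subjects, who may enter with Grade 1 abnormalities. They also have scheduled CD4 counts, though these do not cover neutrophils or eosinophils.

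Finally, the documents point to no specific risk to these counts. Section 12.5 describes the predecessor's events as mainly injection site reactions, and Section 5.3.4 reports only minor, non-adverse clinical pathology changes in mice. A reflex differential is thus a deliberate and legitimate economy. All of this limits the claim, but none of it supplies the missing baseline.

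**Conclusion.** The point stands in limited form. Most subjects will have no baseline neutrophil, lymphocyte or eosinophil count, and changes in these counts within a normal total WBC will usually go unseen. Treatment-emergent laboratory adverse events in these counts (Sections 12.1.1, 12.1.5 and 12.6) therefore cannot be reliably assessed. The laboratory DLT and shift tables are affected only for whichever of these counts Table 20-1 grades.

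The share without a baseline is about 95% to 99% for q between 5% and 20%, provided that exclusion 14 removes abnormal WBC among HIV-negative entrants. Without that proviso, at least 80% lack a baseline and post-dose pair at q = 20% in the fully dependent case. Both figures rest on an assumed q. The gap should be closed because safety is the primary objective and the remedy is cheap.

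**What to change.** In Table 10-1, delete the condition on WBC and report an automated differential with absolute counts on every scheduled haematology sample: screening, Day 1 where drawn, before Dose #2, before Dose #3, and 28 days after Dose #3. Where Day 1 laboratory tests are waived under footnote 20 of the schedule, use the screening value as baseline. Make the same change in the Laboratory Manual, and confirm which of these counts Table 20-1 grades so that Sections 7.5.1, 10.3.1 and 12.6 agree.

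The cost is a one-line amendment, a small per-test charge and a few more incidental abnormal values to review. No visit is added and no extra blood should be needed, because haematology is already drawn at these times.

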#### Table 10-2: Clinical Chemistry Panel

Glucose	Alanine aminotransferase (ALT)
Urea	Aspartate aminotransferase (AST)
Creatinine	Alkaline phosphatase (AP)
	Lactate dehydrogenase (LDH)
	Creatine phosphokinase (CK)

Total bilirubin Total protein Albumin

#### Table 10-3. Coagulation Panel

International normalized ratio (INR)

#### Table 10-4. Urinalysis

Specific gravity, pH, ketones, glucose, protein, blood (commercial dipstick may be used); microscopic examination, including quantitation of WBC and RBC;

#### 10.3.2 HIV Monitoring Tests

Quantitative HIV viral load (sensitivity, 20 copies/mL; Ampliprep Taqman®, Roche or comparable commercial assay approved by the Sponsor); CD4 lymphocyte count.

#### 10.3.3 Screening Serologic Tests

The following serology tests will be performed at screening: Hepatitis B surface antigen (HBsAg), antibody to hepatitis C virus, antibody to HIV-1 and HIV-2.

**Confidential and Proprietary** 

[name] 5/31/15 10:25 AM Deleted: Table 2-2 [name] 5/31/15 10:25 AM Deleted: Table 2-3

Page 42 of 75

Date: 30 March 2015

Examples of suitable HIV antibiody tests include: Vitros Anti-HIV 1 + 2 test, Ortho Clinical Diagnostics, Rochester, NY; or Clearview HIV1/2 STAT-PAK (Alere North America, Inc; Orlando, FL. Additional tests may be approved at the discretion of the Sponsor.

### 10.3.4 Pregnancy Tests

For all females, pregnancy ( $\beta$ -hCG) testing will be conducted as scheduled. A negative pregnancy test result must be reported within 24 hours prior to the first dose of study drug.

### 10.4 Reporting of Safety Laboratory Tests

The results of Safety Laboratory Tests will be returned to the Investigator as quickly as possible, typically within 48 hours. Reference ranges (lower limit of normal, upper limit of normal; by sex and age, if appropriate) will be provided for all laboratory analytes.

Procedures for the investigator assessment of laboratory results are detailed in Section 12.1.5.

Procedures for the analysis of laboratory data are described in Section 14.4.

### 10.4.1 Repeating Abnormal Laboratory Tests

Laboratory tests showing abnormal or exclusionary values at screening may be repeated no more than once. After dosing, abnormal laboratory tests assessed as "clinically significant" values may be repeated as often as deemed clinically necessary by the Investigator until the test values return to clinically acceptable limits or until an explanation other than drug effect is given.

### 10.5 Immunogenicity Assessments

### 10.5.1 Preparation and storage of Peripheral Blood Mononuclear Cells (PBMCs)

Whole blood will be collected as scheduled. PBMCs will be isolated using Ficoll density centrifugation within 2 hours of collection. Isolated cells may be used directly for immunogenicity assessments or stored frozen at -70C or lower.

Assay [ref]	Purpose / Rationale	Antigens 	Estimated PBMC/Assay	Estimated blood vol
Multiplex (13 color) intracellular cytokine staining (ICS) assay for IFN-γ, TNF-α and other cytokines [9]	Sensitive assay for cytokine responses to major antigens; patterns define functional T cell response and phenotype	DAR-901 lysate MTb whole cell lysate Medium SEB	4 x 10^6	10 mL
ELISA of 5-day cell culture assayed for IFN-γ [10,11][12]	Assay of cytokine response to major antigens ELISA for IFN-γ used in DarDar trial. b	DAR-901 lysate MTb whole cell lysate Ag 85, ESAT Medium Phytohemagglutinin	3 x 10^6	5 mL
IFN-γ ELISpot [13]	Standard assay that allows scalable assessment of antigen specificity of responses	Medium Phytohemagglutinin DAR-901 lysate MTb whole cell lysate and/or Panel of mycobacterial peptides and lipopeptides	2 x 10  up to 15 x 10  for panel of multiple specific antigens	5 mL
Mycobacterial growth inhibition assay (MGIA) [14,15,16]	Functional assay of PBMC capacity to inhibit growth of mycobacteria. a	N/A	2 x 10^6	5 mL

#### Table 10-5. Immunogenicity assays

RNA analysis (transcriptional profiling)	Defines changes in expression of immune response related- genes		Pax-gene tube	3 mL
Antigen-specific Serum IgG responses by ELISA [10]	Highly sensitive, reproducible assay; assesses T-cell dependent humoral immunity	Lipoarabinomannan	N/A (serum only)	7 mL (for serum)

a. The mycobacterial growth inhibition assay (MGIA) is being evaluated as a potential "marker" of effective vaccination in clinical trials of new TB vaccines. Studies using BCG vaccine in human subjects show that PBMCs from vaccinated individuals result in growth inhibition of live BCG or *Mtb* as measured by the Becton Dickinson MGIT.

b. Among the placebo subjects in the DarDar trial, baseline responses in the IFN-γ cytokine release assay were associated with decreased risk of incident definite tuberculosis.

Note: Aeras will receive PBMCs from 20 mL of blood (PBMCs from each 10 mL into separate cryovial) and Dartmouth from 5 mL of blood. Pax gene tube will also be processed by Aeras

**Estimated blood volume requirements.** The full panel of cellular assays would require  $\sim 24 \times 10^{6}$  PBMCs. For healthy adults, ficoll density gradient centrifugation typically yields 1.3 x 10^6 PBMCs per mL of whole blood. Yields from HIV-infected subjects are more variable, depending on current antiretroviral therapy and other clinical factors, but are usually 0.6 to 1.1 x 10^6 per mL. Thus, the proposed 40 mL would be expected to yield, for healthy volunteers, 52 x 10^6 PBMCs, and for HIV-positive subjects, 24 to 44 x 10^6. Any unused cells will be retained for up to two years for supplemental assays.

Comments. In assessing immunogenicity, primary emphasis will be given to two antigen-specific assays:

- IFN-γ stimulation by ELISpot in response to mycobacterial antigens
- IFN-γ production in response to DAR-901 lysate in PBMC culture supernatants

The 13-color ICS assay and the IFN-γ ELISpot assay will be conducted at Aeras' immunology laboratory using frozen PBMC. The reagents, equipment, and training of personnel have been standardized, and both assays are being qualified for use in vaccine trials. Conducting these assays in single laboratory reduces assay variability and is particularly critical for determining the correlation between the two assays.

Cytokine release by cultured PBMCs was the primary immunologic assessment used in the DarDar trial (see Section 5.5.6)[10, 11].

RNA transcriptional analysis is an exploratory assessment at this time. It offers the potential to assess changes in the expression of genes related to both innate and adaptive immunity and to identify the activation of specific intracellular pathways.

The mycobacterial growth inhibition assay (MGIA) is currently being developed by Aeras with the potential for qualification as a new method to directly assess the ability of PBMCs to inhibit mycobacterial growth. Assays from all 6 timepoints will be conducted at the same time on frozen PBMCs.

Page 45 of 75 Date: 30 March 2015

# **11. STUDY EVENTS**

Detailed schedules of evaluations are shown Section 2.9; Table 2-4, gives an estimate of blood volumes required. The schedule is presented relative to the day and time of dosing. All Days are relative to day of first injection of study drug, designated Day 1; all times are relative to the most recent injection, designated 0 hr.

# Monitoring for adverse events and concomitant medications will be performed on an ongoing basis from screening through End-of-Study visit.

### 11.1 Screening

The screening evaluation may be performed up to 28 days prior to dosing. The subject will sign an Informed Consent Form before any study-specific procedures are performed. The IRB approved Informed Consent Form (ICF) will be provided on electronic tablets which hold the source documents for the study.

The subjects will be able to review the informed consents on the tablet or they can receive a paper copy of the form to review. Signatures on the ICF will be made on a printed copy and then uploaded to the electronic tablets. The subjects will receive a printed version of the signed informed consent for their records. A PDF of the informed consent will be added to the subject's Electronic Health Record. Data from each subject that signs an informed consent form will be maintained within the electronic Source system (Clinical Ink).

